9.4.4 SAFETY ANALYSES

Side effects measured by the Patient-Rated Inventory of Side Effects (PRISE) will be reported descriptively using the number and percentage of patients with each reported side effect. Psychotomimetic, dissociative, and manic symptoms experienced on infusion days, measured by the Clinician-Administered Dissociative States Scale (CADSS), the Brief Psychiatric Rating Scale (BPRS), and the first item (elevated mood) of the Young Mania Rating Scale (YMRS) will also be reported descriptively. The distribution of suicide risk (low, moderate or high) as measured by the Columbia-Suicide Severity Rating Scale (C-SSRS) will be reported by visit descriptively.

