1.3 SCHEDULE OF ACTIVITIES (SOA)

Procedures	Screening	Baseline	Ketamine Infusions	24 hour Follow-Up Visit	Assessment of Response to Ketamine	WET Sessions	Weekly Assessment Until 12 weeks	Monthly Assessment Until Loss-of-Response
	Day - 28 to 0	Visit 1a, Day 1	Visit 1a-9; Days 1, 3, 5, 8, 11, 12	Visit 1b, Day 2	Visit 5, Day 9	Visit 6-12, Days 10, 12, 16, 18, 22	Visits 10, 13-23, Days 12, 19, 26...	Visits 23-26, Days 33...
Informed consent	x							
Demographics	x							
Medical history	x							
SCID-5	x							
CAPS-5	x	x			x		x	x
MADRS	x	x			x		x	x
WTAR	x							
MoCA	x							
IES-R		x	x	x	x			
QIDS-SR		x	x	x	x			
PCL-5	x	x			x		x	x
MOS-5		x					x ¹	
CES		x					x ¹	
PACT		x					x ¹	
CTQ	x							
TLEQ	x							
SDS	x	x		x	x		x	x
HMS			x ²					
PIQ			x ²					
C-SSRS	x	x			x		x	x
CADSS		x	x					
BPRS		x	x					
YMRS		x	x					
Extinction Learning Task	x				x			
CGI	x	x	x	x	x		x	x
Concomitant medication review	x	x	x	x	x		x	x
PRISE	x	x	x	x	x		x	x

Adverse event review and evaluation	x	x	x	x	x	x	x	x
Physical exam (including height and weight)	x							
Vital signs	x		x					
Weight	x		x					
EKG	x							
Routine labs	x							
Plasma ketamine and norketamine levels			x ³					
Urine pregnancy test	x		x					
Urine drug screen (UTOX)	x		x					
Ketamine infusion (0.5 mg/kg)			x					
Written Exposure Therapy (WET)						x		
Complete Case Report Forms (CRFs)	x	x	x	x	x	x	x	x

¹Visit 14 and 23 only

²only at Infusions 1 and 2

³only at Infusion 1

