Secondary outcome measures (exploratory): The CAPS-5 will be administered weekly (beginning at baseline prior to the first ketamine infusion) until 6 weeks from the start of WET; thereafter, the CAPS-5 will be administered weekly as tolerated until 12 weeks; all participants will be administered the CAPS-5 at the 12-week time point. Participants who maintain PTSD symptom improvement after 12 weeks will be assessed monthly up to 24 weeks from the start of WET or until loss of improvement, by the blinded clinical rater. The PCL-5 and SDS (self-report scales), the MADRS (administered by the blinded clinical rater), and the CGI-S and CGI-Improvement scales (administered by a study psychiatrist or clinician) will be administered at the same time points until 12 weeks, and then monthly up to 24 weeks or until loss of improvement (See **3.1 Schedule of Activities**). The Quick Inventory of Depressive Symptomatology-Self-Report version (QIDS-SR)⁶⁶ and the Impact of Events Scale-Revised (IES-R),⁶⁷ both self-report scales, will be administered at baseline, 24 hours after the first infusion, at each infusion visit, and on the day of response to ketamine assessment, to capture any ketamine-related rapid changes in symptom levels. An abbreviated version of the Medical Outcomes Study Social Support Survey (MOS-SSS),⁶⁸ the Centrality of Event Scale (CES),⁶⁹ and the Perceived Ability to Cope with Trauma Scale (PACT)⁷⁰ will be administered at baseline (prior to any infusions) and again 3 weeks after the first WET session; data from these scales will be used for Aim-3 analyses.

Safety Assessments: Participants will be evaluated prior to each infusion by the PI or another study-affiliated psychiatrist; including review of vital signs, weight/BMI, drug and pregnancy tests, concomitant medications and adverse events. Participants will be monitored continuously during all ketamine infusions. On infusion days, side effects will be assessed with the Patient-Rated Inventory of Side Effects (PRISE) Adverse Event Visit Checklist,⁷¹ the Clinician-Administered Dissociative States Scale (CADSS),⁷² the Brief Psychiatric Rating Scale (BPRS) 4 items assessing positive symptoms,⁷³ and the Young Mania Rating Scale first item.⁷⁴

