Note: Concurrent treatment with other psychotropic medications (including a short-acting benzodiazepine at bedtime only) will be permitted, but dose must be stabilized for at least three months before study start.

* Potential participants will not be told to discontinue medication for the purposes of this study if there is any evidence that the medication is clinically beneficial. Further, a study physician will not taper a potential participant off of a medication; rather, this may only be completed by the prescribing physician. This is our policy across all of our studies.

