8.2 SAFETY AND OTHER ASSESSMENTS

Participants in this proposed study will provide the following safety data:

- (A) Data related to medical history, physical examination including review of systems, vital signs, ECG, routine laboratory tests (comprehensive metabolic panel, complete blood count, thyroid function testing) needed to determine eligibility and to monitor safety of participants
- (B) Measures to assess for any acute side effects associated with ketamine before and after each infusion; potential longer- lasting side effects will be assessed weekly until resolution.

For laboratory tests, all results will be reviewed by the PI or study-affiliated psychiatrist, and any incidental finding will be conveyed to the subject with provision for additional work-up if needed.

Plasma ketamine and norketamine levels will be assessed via serial blood draws at the first ketamine infusion. Blood will be drawn from a second IV catheter at 30, 60, 90, and 120 minutes from the start of the infusion. Samples will be spun down and aliquoted into plasma samples. These samples will then be transported to Mount Sinai Clinical Laboratory Services (Sinai Labs) for shipment to an external laboratory (LabCorps) for the ketamine and norketamine levels.

The **Patient-Rated Inventory of Side Effects (PRISE)** Adverse Event Visit Checklist⁷¹ is a clinician-administered questionnaire used to qualify side effects by identifying and evaluating the tolerability of each symptom. This scale will be completed before and after each infusion, and at each assessment time point (weekly until 12 weeks, and then monthly up to 24 weeks or until loss of response), by the PI or another study psychiatrist.

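### Section 9.4.4 counts PRISE side effects without comparing them with the ratings taken before ketamine, so persisting earlier symptoms can be counted as side effects of treatment.

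*Combined protocol and SAP*

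**What the plan says.** Section 9.4.4 (Safety Analyses) gives the whole PRISE analysis in one sentence: side effects "will be reported descriptively using the number and percentage of patients with each reported side effect". It names no reference rating and no threshold for worsening.

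PRISE is collected well before treatment and often during it. The Schedule of Activities (Section 1.3) marks it at screening, at baseline, on infusion days, at the 24-hour visit, at the response assessment after the fourth infusion, and at the weekly and monthly assessments. Section 8.2 says: "This scale will be completed before and after each infusion, and at each assessment time point". The same section describes the instrument as "identifying and evaluating the tolerability of each symptom".

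Section 5.2 allows other psychotropic drugs: they "will be permitted, but dose must be stabilized for at least three months before study start". Section 9.3 places all participants in the safety dataset, Section 9.2 enrols up to 15, and Section 6.3 confirms that everyone receives the same open-label treatment.

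**The concern.** A PRISE item can be reported because of the illness, because of a stable background drug, or because of ketamine or WET. Participants have chronic PTSD, often with depressive symptoms, and some will be on long-standing psychotropic medication, so some items are likely to be present at screening. A symptom that persists unchanged will be reported again after ketamine, and a raw count of patients treats that report in the same way as a new one.

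In a randomised trial the control arm would show this background. Here the only available reference is the participant's own rating before ketamine, and the planned summary does not use it. A reader of the published table could not tell how much of an item's percentage arose after treatment began. What is at stake is the interpretation of the side-effect table for a new combined treatment.

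**Working it through.** The plan states no figure for this count, so there is nothing to reproduce. The check sets the sections side by side and then shows what can and cannot be quantified.

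**1. Are there ratings before ketamine?** Yes. In Section 1.3 PRISE is marked in 7 of 8 columns, and 2 of those 7 (screening and baseline) precede any ketamine. The infusion column is headed "Visit 1a-9; Days 1, 3, 5, 8, 11, 12". Six infusions with a rating on each side give 6 × 2 = 12 ratings on infusion days. Of these, 6 come before an infusion and 1 (Day 1) comes before all ketamine. Baseline is also Day 1, so that rating and the baseline rating may be the same one.

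**2. Does restricting the visits solve the problem?** No.
- All visits: reports made before ketamine enter directly.
- Infusion days only: Section 4.1 would support this, since "On infusion days, side effects will be assessed with the Patient-Rated Inventory of Side Effects (PRISE) Adverse Event Visit Checklist". The Day 1 rating before infusion still enters, and so do persisting symptoms.
- Ratings after the first infusion only: the early ratings drop out, but a symptom that persists is reported again and counted.

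**3. Does another section supply the missing comparison?**
- Section 8.3.4 treats conditions present at screening as baseline and records deterioration, but it governs what is recorded as an adverse event. Section 9.4.4 tabulates PRISE items.
- Section 8.3.3.2 grades the causality of adverse events. No such step is stated for PRISE items.
- Section 9.4.1 defines change from the pre-WET day. That day follows four infusions, so it cannot identify symptoms present before ketamine.

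**4. Size.** For one item, let p0 be the proportion reporting it before ketamine, s the share of those who report it again afterwards, w the share of those repeat reporters in whom it became worse, and q the proportion of the remaining participants who newly report it.
- Raw percentage after ketamine = p0·s + (1 − p0)·q
- New-or-worse percentage = p0·s·w + (1 − p0)·q
- Excess = p0·s·(1 − w)

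The documents give none of p0, s, w or q, so the excess cannot be computed. As an illustration on assumed values only, take s = 1 and w = 0, the case with the largest excess, with p0 from 20% to 60% and q from 10% to 30%:

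| p0 | q | Raw | New or worse | Excess |
|---|---|---|---|---|
| 20% | 10% | 28% | 8% | 20 points |
| 20% | 30% | 44% | 24% | 20 points |
| 60% | 10% | 64% | 4% | 60 points |
| 60% | 30% | 72% | 12% | 60 points |

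The excess here equals the assumed p0, so the table shows how the error works and does not estimate its size. The only figure that follows from the plan is the weight of one person: 1/15 = 6.7 percentage points with the full 15, and more if fewer enrol. That weight applies to any percentage in a sample of this size.

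**The case against.** The strongest reply is that a side effect cannot precede the drug. Section 8.2 describes these measures as capturing acute effects around each infusion, with longer-lasting effects followed weekly. On that reading the table would naturally use reports made after ketamine, with earlier ratings as the reference. A table by visit would also comply with Section 9.4.4 and would show the baseline column.

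Part of this stands. A reader might infer that Section 9.4.4 requires pooling over all visits, including screening. The text does not say so. A reader might also infer that PRISE is singled out because the paragraph limits other scales to "Psychotomimetic, dissociative, and manic symptoms experienced on infusion days" and says the C-SSRS distribution "will be reported by visit descriptively". That contrast carries little weight: CADSS, BPRS and the YMRS item are also rated before infusions and have no new-or-worse rule either. A missing time window alone would only be missing detail.

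The reply does not reach the remaining point. Excluding earlier visits does not remove symptoms that persist into later ones, and nothing in the plan says that the earlier ratings will serve as the reference for the count.

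It can also be said that new or worse safety information is captured elsewhere. PRISE is titled as an adverse event checklist and completed by a psychiatrist, and the DSMB receives adverse event summaries by type, severity and treatment phase (Sections 8.3.5 and 10.1.6). This is correct and limits the consequence, but adverse event review is a separate row in Section 1.3 and those rules do not define the PRISE table. Finally, any error overstates harm and does not hide it, which also keeps the point minor.

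**Conclusion.** The concern holds in limited form and is minor. As written, the PRISE percentages can include persisting symptoms that were present before ketamine, even if only ratings after ketamine are used. They can therefore overstate side effects by an amount that the documents do not allow to be computed. The conclusion assumes only that some participants report an item before ketamine and report it again later without worsening.

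A reader might go further and infer that the adverse event record, participant protection or the efficacy estimates are compromised. The documents do not support this: adverse events have their own baseline rule and causality grading, and the CAPS-5 analysis does not use PRISE.

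**What to change.** Add to Section 9.4.4 that a PRISE item is counted as treatment-emergent only if, after the start of the first infusion, it is newly reported or less well tolerated than at the worst rating before ketamine (screening, baseline or Day 1 before infusion). Taking the worst of these settles the reference when they differ. Section 8.2 indicates that tolerability is evaluated but gives no grading levels; if the form does not grade it, the rule should be newly reported only. Beside each count, show the number and percentage reporting the item before ketamine.

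The cost is two or three sentences in the plan and a few lines of analysis, with no new data, visits or staff. The raw any-report figure is no longer the headline, but it can be kept as a listing. Separate tables by type of visit and a named adverse event table are optional.

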9.4.5 BASELINE DESCRIPTIVE STATISTICS

Patient demographics and baseline characteristics will be summarized using mean and standard deviation or median and interquartile range as appropriate for continuous measures, and number and percentage for categorical measures.

9.4.6 PLANNED INTERIM ANALYSES

Not applicable.

9.4.7 SUB-GROUP ANALYSES

Not applicable.

9.4.8 TABULATION OF INDIVIDUAL PARTICIPANT DATA

Not applicable.

9.4.9 EXPLORATORY ANALYSES

Secondary efficacy endpoint analyses and Aim 2 analyses are exploratory (see details above).

10 SUPPORTING DOCUMENTATION AND OPERATIONAL CONSIDERATIONS

10.1 REGULATORY, ETHICAL, AND STUDY OVERSIGHT CONSIDERATIONS

10.1.1 INFORMED CONSENT PROCESS

10.1.1.1 CONSENT/ASSENT AND OTHER INFORMATIONAL DOCUMENTS PROVIDED TO PARTICIPANTS

Consent forms describing in detail the study intervention, study procedures, and risks are given to the participant and written or electronic documentation of informed consent is required prior to starting intervention/administering study intervention. The following consent materials are submitted with this protocol: HRP-502a, documentation of informed consent.

10.1.1.2 CONSENT PROCEDURES AND DOCUMENTATION

After completing the screening process at DAC through protocol STUDY-10-00606, potentially eligible participants will be invited to participate in a screening visit for this protocol. Informed consent may be obtained in person or remotely, using a HIPAA-compliant telehealth platform(e.g., VSee, Doximity, HIPAA-Zoom) and the electronic consent survey housed on REDCap. As the proposed study involves ketamine infusions, the informed consent will be obtained by either the PI or one of the study-affiliated psychiatrists. Consent may be obtained by a clinical research coordinator prior to administering clinical rating scales, self-report scales, the extinction learning task, and/or the medical clearance assessment. In this case, the PI or study-affiliated psychiatrist will re-review the consent form with the participant and will co-sign the form prior to the participant beginning the first study intervention (ketamine infusions). Potential participants will be informed about possible alternatives to participating in the study. A release of information will be obtained for review of any available historical and clinical data. Authorization is also obtained from each subject in the consent document, permitting the research team to use, create, or disclose the subject's PHI for research purposes. The nature of the project, procedures, relative risks and benefits, and alternatives to participation in the project will be discussed with the individual. The individual will be given ample opportunity to ask any questions they might have. Following this discussion, the individual will be given a physical or electronic copy of the consent form to review at their leisure, and any remaining questions will be answered. If the individual remains interested in the project, written or electronic informed consent is obtained, and medical and psychiatric screening procedures are undertaken to confirm eligibility. If the individual decides not to participate in this study, a staff member provides reasonable and timely assistance in obtaining an alternative referral, if so desired. The decision not to participate does not affect eligibility to participate in future studies, to receive treatment at Mount Sinai or at any program serving PTSD populations, or to receive treatment on a private basis. Subjects will be also be given the opportunity to withdraw from the study at any point. The consent process also includes documentation of permission to obtain previous medical records, including contact with previous physicians, pharmacies, and family members.

10.1.2 STUDY DISCONTINUATION AND CLOSURE

This study may be temporarily suspended or prematurely terminated if there is sufficient reasonable cause. Written notification, documenting the reason for study suspension or termination, will be provided by the suspending or terminating party to study participants, investigator, and regulatory authorities. If the study is prematurely terminated or suspended, the Principal Investigator (PI) will

promptly inform study participants, the Institutional Review Board (IRB), and sponsor and will provide the reason(s) for the termination or suspension. Study participants will be contacted, as applicable, and be informed of changes to study visit schedule.

Circumstances that may warrant termination or suspension include, but are not limited to:

- Determination of unexpected, significant, or unacceptable risk to participants
- Demonstration of efficacy that would warrant stopping
- Insufficient compliance to protocol requirements
- Data that are not sufficiently complete and/or evaluable
- Determination that the primary endpoint has been met
- Determination of futility

Study may resume once concerns about safety, protocol compliance, and data quality are addressed, and satisfy the sponsor, IRB and/or Food and Drug Administration (FDA).

10.1.3 CONFIDENTIALITY AND PRIVACY

Participant confidentiality and privacy is strictly held in trust by the participating investigators, their staff, and the sponsor(s) and their interventions. This confidentiality is extended to cover testing of biological samples and genetic tests in addition to the clinical information relating to participants. Therefore, the study protocol, documentation, data, and all other information generated will be held in strict confidence. No information concerning the study or the data will be released to any unauthorized third party without prior written approval of the sponsor.

All research activities will be conducted in as private a setting as possible. Prior to beginning any study procedures conducted remotely via HIPAA-compliant telehealth video platform (e.g., clinical assessment, delivery of a WET session), study personnel will first confirm with the participant that he/she is situated in a private room at home, with no other persons present in the room, to ensure privacy and confidentiality.

The study monitor, other authorized representatives of the sponsor, representatives of the Institutional Review Board (IRB), regulatory agencies or pharmaceutical company supplying study product may inspect all documents and records required to be maintained by the investigator, including but not limited to, medical records (office, clinic, or hospital) and pharmacy records for the participants in this study. The clinical study site will permit access to such records.

The study participant's contact information will be securely stored at each clinical site for internal use during the study. At the end of the study, all records will continue to be kept in a secure location for as long a period as dictated by the reviewing IRB, Institutional policies, or sponsor requirements.

Study participant research data, which is for purposes of statistical analysis and scientific reporting, will be transmitted to and stored at the ISMMS. This will not include the participant's contact or identifying information. Rather, individual participants and their research data will be identified by a unique study identification number. The study data entry and study management systems used by the clinical site and by ISMMS research staff will be secured and password protected. At the end of the study, all study databases will be de-identified and archived at the ISMMS.

Certificate of Confidentiality

To further protect the privacy of study participants, a Certificate of Confidentiality has been issued by the National Institutes of Health (NIH). This certificate protects identifiable research information from forced disclosure. It allows the investigator and others who have access to research records to refuse to disclose identifying information on research participation in any civil, criminal, administrative, legislative, or other proceeding, whether at the federal, state, or local level. By protecting researchers and institutions from being compelled to disclose information that would identify research participants, Certificates of Confidentiality help achieve the research objectives and promote participation in studies by helping assure confidentiality and privacy to participants.

10.1.4 FUTURE USE OF STORED SPECIMENS AND DATA

Data collected for this study will be analyzed and stored at the ISMMS.

Blood samples will be collected for routine clinical labs at screening (medical clearance) and study exit, and to measure plasma ketamine and norketamine during the first ketamine infusion. No specimens will be stored for future use.

When the study is completed, access to de-identified study data should be requested by contacting the PI, [name].

